Hearing Loss ≥ 12 years of age	NA	Hearing aid or intervention not indicated	Hearing aid or intervention indicated	Profound bilateral hearing loss (> 80 dB at 2 kHz and above) OR Non-serviceable hearing (i.e., >50 dB audiogram and <50% speech discrimination)
< 12 years of age (based on a 1, 2, 3, 4, 6 and 8 kHz audiogram)	> 20 dB hearing loss at ≤ 4 kHz	> 20 dB hearing loss at > 4 kHz	> 20 dB hearing loss at ≥ 3 kHz in one ear with additional speech language related services indicated (where available) OR Hearing loss sufficient to indicate therapeutic intervention, including hearing aids	Audiologic indication for cochlear implant and additional speech-language related services indicated (where available)
Tinnitus	Symptoms causing no or minimal interference with usual social & functional activities with intervention not indicated	Symptoms causing greater than minimal interference with usual social & functional activities with intervention indicated	Symptoms causing inability to perform usual social & functional activities	NA
Uveitis	No symptoms AND Detectable on examination	Anterior uveitis with symptoms OR Medical intervention indicated	Posterior or pan-uveitis OR Operative intervention indicated	Disabling visual loss in affected eye(s)
Vertigo	Vertigo causing no or minimal interference with usual social & functional activities	Vertigo causing greater than minimal interference with usual social & functional activities	Vertigo causing inability to perform usual social & functional activities	Disabling vertigo causing inability to perform basic self-care functions
Visual Changes (assessed from baseline)	Visual changes causing no or minimal interference with usual social & functional activities	Visual changes causing greater than minimal interference with usual social & functional activities	Visual changes causing inability to perform usual social & functional activities	Disabling visual loss in affected eye(s)

Systemic

PARAMETER	GRADE 1 MILD	GRADE 2 MODERATE	GRADE 3 SEVERE	GRADE 4 POTENTIALLY LIFE- THREATENING
Acute Allergic Reaction	Localized urticaria (wheals) with no medical intervention indicated	Localized urticaria with intervention indicated OR Mild angioedema with no intervention indicated	Generalized urticaria OR Angioedema with intervention indicated OR Symptoms of mild bronchospasm	Acute anaphylaxis OR Life-threatening bronchospasm OR Laryngeal edema
Chills	Symptoms causing no or minimal interference with usual social & functional activities	Symptoms causing greater than minimal interference with usual social & functional activities	Symptoms causing inability to perform usual social & functional activities	NA
Cytokine Release Syndrome⁸	Mild signs and symptoms AND Therapy (i.e., antibody infusion) interruption not indicated	Therapy (i.e., antibody infusion) interruption indicated AND Responds promptly to symptomatic treatment OR Prophylactic medications indicated for ≤ 24 hours	Prolonged severe signs and symptoms OR Recurrence of symptoms following initial improvement	Life-threatening consequences (e.g., requiring pressor or ventilator support)
Fatigue or Malaise Report only one	Symptoms causing no or minimal interference with usual social & functional activities	Symptoms causing greater than minimal interference with usual social & functional activities	Symptoms causing inability to perform usual social & functional activities	Incapacitating symptoms of fatigue or malaise causing inability to perform basic self-care functions
Fever (non-axillary temperatures only)	38.0 to $< 38.6^{\circ}\text{C}$ or 100.4 to $< 101.5^{\circ}\text{F}$	≥ 38.6 to $< 39.3^{\circ}\text{C}$ or ≥ 101.5 to $< 102.7^{\circ}\text{F}$	≥ 39.3 to $< 40.0^{\circ}\text{C}$ or ≥ 102.7 to $< 104.0^{\circ}\text{F}$	$\geq 40.0^{\circ}\text{C}$ or $\geq 104.0^{\circ}\text{F}$
Pain⁹ (not associated with study agent injections and not specified elsewhere) Specify location	Pain causing no or minimal interference with usual social & functional activities	Pain causing greater than minimal interference with usual social & functional activities	Pain causing inability to perform usual social & functional activities	Disabling pain causing inability to perform basic self-care functions OR Hospitalization indicated

⁸ Definition: A disorder characterized by nausea, headache, tachycardia, hypotension, rash, and/or shortness of breath.

⁹ For pain associated with injections or infusions, see the *Site Reactions to Injections and Infusions* section

Systemic

PARAMETER	GRADE 1 MILD	GRADE 2 MODERATE	GRADE 3 SEVERE	GRADE 4 POTENTIALLY LIFE- THREATENING
Serum Sickness ¹⁰	Mild signs and symptoms	Moderate signs and symptoms AND Intervention indicated (e.g., antihistamines)	Severe signs and symptoms AND Higher level intervention indicated (e.g., steroids or IV fluids)	Life-threatening consequences (e.g., requiring pressor or ventilator support)
Underweight ¹¹ > 5 to 19 years of age	WHO BMI z-score < -1 to -2	WHO BMI z-score < -2 to -3	WHO BMI z-score < -3	WHO BMI z-score < -3 with life-threatening consequences
2 to 5 years of age	WHO BMI z-score < -1 to -2	WHO Weight-for-height z-score < -2 to -3	WHO Weight-for-height z-score < -3	WHO Weight-for-height z-score < -3 with life-threatening consequences
< 2 years of age	WHO BMI z-score < -1 to -2	WHO Weight-for-length z-score < -2 to -3	WHO Weight-for-length z-score < -3	WHO Weight-for-length z-score < -3 with life-threatening consequences
Unintentional Weight Loss (excludes postpartum weight loss)	NA	5 to < 9% loss in body weight from baseline	≥ 9 to < 20% loss in body weight from baseline	≥ 20% loss in body weight from baseline OR Aggressive intervention indicated (e.g., tube feeding, total parenteral nutrition)

¹⁰ Definition: A disorder characterized by fever, arthralgia, myalgia, skin eruptions, lymphadenopathy, marked discomfort, and/or dyspnea.

¹¹ WHO reference tables may be accessed by clicking the desired age range or by accessing the following URLs:

http://www.who.int/growthref/who2007_bmi_for_age/en/ for participants > 5 to 19 years of age and

http://www.who.int/childgrowth/standards/chart_catalogue/en/ for those ≤ 5 years of age.

Urinary

PARAMETER	GRADE 1 MILD	GRADE 2 MODERATE	GRADE 3 SEVERE	GRADE 4 POTENTIALLY LIFE- THREATENING
Urinary Tract Obstruction	NA	Signs or symptoms of urinary tract obstruction without hydronephrosis or renal dysfunction	Signs or symptoms of urinary tract obstruction with hydronephrosis or renal dysfunction	Obstruction causing life-threatening consequences

Site Reactions to Injections and Infusions

PARAMETER	GRADE 1 MILD	GRADE 2 MODERATE	GRADE 3 SEVERE	GRADE 4 POTENTIALLY LIFE- THREATENING
Injection Site Pain or Tenderness Report only one	Pain or tenderness causing no or minimal limitation of use of limb	Pain or tenderness causing greater than minimal limitation of use of limb	Pain or tenderness causing inability to perform usual social & functional activities	Pain or tenderness causing inability to perform basic self-care function OR Hospitalization indicated
Injection Site Erythema or Redness¹² Report only one > 15 years of age	2.5 to < 5 cm in diameter OR 6.25 to < 25 cm ² surface area AND Symptoms causing no or minimal interference with usual social & functional activities	≥ 5 to < 10 cm in diameter OR ≥ 25 to < 100 cm ² surface area OR Symptoms causing greater than minimal interference with usual social & functional activities	≥ 10 cm in diameter OR ≥ 100 cm ² surface area OR Ulceration OR Secondary infection OR Phlebitis OR Sterile abscess OR Drainage OR Symptoms causing inability to perform usual social & functional activities	Potentially life-threatening consequences (e.g., abscess, exfoliative dermatitis, necrosis involving dermis or deeper tissue)
≤ 15 years of age	≤ 2.5 cm in diameter	> 2.5 cm in diameter with < 50% surface area of the extremity segment involved (e.g., upper arm or thigh)	≥ 50% surface area of the extremity segment involved (e.g., upper arm or thigh) OR Ulceration OR Secondary infection OR Phlebitis OR Sterile abscess OR Drainage	Potentially life-threatening consequences (e.g., abscess, exfoliative dermatitis, necrosis involving dermis or deeper tissue)
Injection Site Induration or Swelling Report only one > 15 years of age	Same as for Injection Site Erythema or Redness , > 15 years of age	Same as for Injection Site Erythema or Redness , > 15 years of age	Same as for Injection Site Erythema or Redness , > 15 years of age	Same as for Injection Site Erythema or Redness , > 15 years of age
≤ 15 years of age	Same as for Injection Site Erythema or Redness , ≤ 15 years of age	Same as for Injection Site Erythema or Redness , ≤ 15 years of age	Same as for Injection Site Erythema or Redness , ≤ 15 years of age	Same as for Injection Site Erythema or Redness , ≤ 15 years of age
Injection Site Pruritus	Itching localized to the injection site that is relieved spontaneously or in < 48 hours of treatment	Itching beyond the injection site that is not generalized OR Itching localized to the injection site requiring ≥ 48 hours treatment	Generalized itching causing inability to perform usual social & functional activities	NA

¹² Injection Site Erythema or Redness should be evaluated and graded using the greatest single diameter or measured surface area.

Laboratory Values*

Chemistries

PARAMETER	GRADE 1 MILD	GRADE 2 MODERATE	GRADE 3 SEVERE	GRADE 4 POTENTIALLY LIFE- THREATENING
Acidosis	NA	pH \geq 7.3 to $<$ LLN	pH $<$ 7.3 without life-threatening consequences	pH $<$ 7.3 with life-threatening consequences
Albumin, Low (g/dL; g/L)	3.0 to $<$ LLN 30 to $<$ LLN	\geq 2.0 to $<$ 3.0 \geq 20 to $<$ 30	$<$ 2.0 $<$ 20	NA
Alkaline Phosphatase, High	1.25 to $<$ 2.5 x ULN	2.5 to $<$ 5.0 x ULN	5.0 to $<$ 10.0 x ULN	\geq 10.0 x ULN
Alkalosis	NA	pH $>$ ULN to \leq 7.5	pH $>$ 7.5 without life-threatening consequences	pH $>$ 7.5 with life-threatening consequences
ALT or SGPT, High Report only one	1.25 to $<$ 2.5 x ULN	2.5 to $<$ 5.0 x ULN	5.0 to $<$ 10.0 x ULN	\geq 10.0 x ULN
Amylase (Pancreatic) or Amylase (Total), High Report only one	1.1 to $<$ 1.5 x ULN	1.5 to $<$ 3.0 x ULN	3.0 to $<$ 5.0 x ULN	\geq 5.0 x ULN
AST or SGOT, High Report only one	1.25 to $<$ 2.5 x ULN	2.5 to $<$ 5.0 x ULN	5.0 to $<$ 10.0 x ULN	\geq 10.0 x ULN
Bicarbonate, Low (mEq/L; mmol/L)	16.0 to $<$ LLN 16.0 to $<$ LLN	11.0 to $<$ 16.0 11.0 to $<$ 16.0	8.0 to $<$ 11.0 8.0 to $<$ 11.0	$<$ 8.0 $<$ 8.0
Bilirubin Direct Bilirubin¹³, High > 28 days of age	NA	NA	$>$ ULN with other signs and symptoms of hepatotoxicity.	$>$ ULN with life-threatening consequences (e.g., signs and symptoms of liver failure)
\leq 28 days of age	ULN to \leq 1 mg/dL	$>$ 1 to \leq 1.5 mg/dL	$>$ 1.5 to \leq 2 mg/dL	$>$ 2 mg/dL
Total Bilirubin, High > 28 days of age	1.1 to $<$ 1.6 x ULN	1.6 to $<$ 2.6 x ULN	2.6 to $<$ 5.0 x ULN with other signs and symptoms of hepatotoxicity.	\geq 5.0 x ULN with life-threatening consequences (e.g., signs and symptoms of liver failure).
\leq 28 days of age	See Appendix A. Total Bilirubin for Term and Preterm Neonates	See Appendix A. Total Bilirubin for Term and Preterm Neonates	See Appendix A. Total Bilirubin for Term and Preterm Neonates	See Appendix A. Total Bilirubin for Term and Preterm Neonates

*Reminder: An asymptomatic abnormal laboratory finding without an accompanying AE should not be reported to DAIDS in an expedited time frame unless it meets protocol-specific reporting requirements.

¹³ Direct bilirubin $>$ 1.5 mg/dL in a participant $<$ 28 days of age should be graded as grade 2, if $<$ 10% of the total bilirubin.

Chemistries

PARAMETER	GRADE 1 MILD	GRADE 2 MODERATE	GRADE 3 SEVERE	GRADE 4 POTENTIALLY LIFE- THREATENING
Calcium, High (mg/dL; mmol/L) ≥ 7 days of age	10.6 to < 11.5 2.65 to < 2.88	11.5 to < 12.5 2.88 to < 3.13	12.5 to < 13.5 3.13 to < 3.38	≥ 13.5 ≥ 3.38
< 7 days of age	11.5 to < 12.4 2.88 to < 3.10	12.4 to < 12.9 3.10 to < 3.23	12.9 to < 13.5 3.23 to < 3.38	≥ 13.5 ≥ 3.38
Calcium (Ionized), High (mg/dL; mmol/L)	> ULN to < 6.0 > ULN to < 1.5	6.0 to < 6.4 1.5 to < 1.6	6.4 to < 7.2 1.6 to < 1.8	≥ 7.2 ≥ 1.8
Calcium, Low (mg/dL; mmol/L) ≥ 7 days of age	7.8 to < 8.4 1.95 to < 2.10	7.0 to < 7.8 1.75 to < 1.95	6.1 to < 7.0 1.53 to < 1.75	< 6.1 < 1.53
< 7 days of age	6.5 to < 7.5 1.63 to < 1.88	6.0 to < 6.5 1.50 to < 1.63	5.50 to < 6.0 1.38 to < 1.50	< 5.50 < 1.38
Calcium (Ionized), Low (mg/dL; mmol/L)	< LLN to 4.0 < LLN to 1.0	3.6 to < 4.0 0.9 to < 1.0	3.2 to < 3.6 0.8 to < 0.9	< 3.2 < 0.8
Cardiac Troponin I, High	NA	NA	NA	Levels consistent with myocardial infarction or unstable angina as defined by the local laboratory
Creatine Kinase, High	3 to < 6 x ULN	6 to < 10x ULN	10 to < 20 x ULN	≥ 20 x ULN
Creatinine, High *Report only one	1.1 to 1.3 x ULN	> 1.3 to 1.8 x ULN OR Increase to 1.3 to < 1.5 x participant's baseline	> 1.8 to < 3.5 x ULN OR Increase to 1.5 to < 2.0 x participant's baseline	≥ 3.5 x ULN OR Increase of ≥ 2.0 x participant's baseline
Creatinine Clearance¹⁴ or eGFR, Low *Report only one	NA	< 90 to 60 ml/min or ml/min/1.73 m ² OR 10 to < 30% decrease from participant's baseline	< 60 to 30 ml/min or ml/min/1.73 m ² OR 30 to < 50% decrease from participant's baseline	< 30 ml/min or ml/min/1.73 m ² OR ≥ 50% decrease from participant's baseline or dialysis needed
Glucose (mg/dL; mmol/L) Fasting, High	110 to 125 6.11 to < 6.95	> 125 to 250 6.95 to < 13.89	> 250 to 500 13.89 to < 27.75	≥ 500 ≥ 27.75
Nonfasting, High	116 to 160 6.44 to < 8.89	> 160 to 250 8.89 to < 13.89	> 250 to 500 13.89 to < 27.75	≥ 500 ≥ 27.75

¹⁴ Use the applicable formula (i.e., Cockcroft-Gault in mL/min or Schwartz, MDRD, CKD-Epi in mL/min/1.73m²). Sites should choose the method defined in their study and when not specified, use the method most relevant to the study population.

*Reminder: Choose the method that selects for the higher grade.

Chemistries

PARAMETER	GRADE 1 MILD	GRADE 2 MODERATE	GRADE 3 SEVERE	GRADE 4 POTENTIALLY LIFE- THREATENING
Glucose, Low (mg/dL; mmol/L) ≥ 1 month of age	55 to 64 3.05 to <3.55	40 to <55 2.22 to < 3.05	30 to <40 1.67 to < 2.22	<30 < 1.67
< 1 month of age	50 to 54 2.78 to < 3.00	40 to <50 2.22 to < 2.78	30 to <40 1.67 to < 2.22	<30 < 1.67
Lactate, High	ULN to < 2.0 x ULN without acidosis	≥ 2.0 x ULN without acidosis	Increased lactate with pH < 7.3 without life- threatening consequences	Increased lactate with pH < 7.3 with life- threatening consequences
Lipase, High	1.1 to < 1.5 x ULN	1.5 to < 3.0 x ULN	3.0 to < 5.0 x ULN	≥ 5.0 x ULN
Lipid Disorders (mg/dL; mmol/L)				
Cholesterol, Fasting, High ≥ 18 years of age	200 to < 240 5.18 to < 6.19	240 to < 300 6.19 to < 7.77	≥ 300 ≥ 7.77	NA
< 18 years of age	170 to < 200 4.40 to < 5.15	200 to < 300 5.15 to < 7.77	≥ 300 ≥ 7.77	NA
LDL, Fasting, High ≥ 18 years of age	130 to < 160 3.37 to < 4.12	160 to < 190 4.12 to < 4.90	≥ 190 ≥ 4.90	NA
> 2 to < 18 years of age	110 to < 130 2.85 to < 3.34	130 to < 190 3.34 to < 4.90	≥ 190 ≥ 4.90	NA
Triglycerides, Fasting, High	150 to 300 1.71 to 3.42	>300 to 500 >3.42 to 5.7	>500 to < 1,000 >5.7 to 11.4	> 1,000 > 11.4
Magnesium¹⁵, Low (mEq/L; mmol/L)	1.2 to < 1.4 0.60 to < 0.70	0.9 to < 1.2 0.45 to < 0.60	0.6 to < 0.9 0.30 to < 0.45	< 0.6 < 0.30
Phosphate, Low (mg/dL; mmol/L) > 14 years of age	2.0 to < LLN 0.65 to < LLN	1.4 to < 2.0 0.45 to < 0.65	1.0 to < 1.4 0.32 to < 0.45	< 1.0 < 0.32
1 to 14 years of age	3.0 to < 3.5 0.97 to < 1.13	2.5 to < 3.0 0.81 to < 0.97	1.5 to < 2.5 0.48 to < 0.81	< 1.5 < 0.48
< 1 year of age	3.5 to < 4.5 1.13 to < 1.45	2.5 to < 3.5 0.81 to < 1.13	1.5 to < 2.5 0.48 to < 0.81	< 1.5 < 0.48
Potassium, High (mEq/L; mmol/L)	5.6 to < 6.0 5.6 to < 6.0	6.0 to < 6.5 6.0 to < 6.5	6.5 to < 7.0 6.5 to < 7.0	≥ 7.0 ≥ 7.0
Potassium, Low (mEq/L; mmol/L)	3.0 to < 3.4 3.0 to < 3.4	2.5 to < 3.0 2.5 to < 3.0	2.0 to < 2.5 2.0 to < 2.5	< 2.0 < 2.0

¹⁵ To convert a magnesium value from mg/dL to mmol/L, laboratories should multiply by 0.4114.

Chemistries

PARAMETER	GRADE 1 MILD	GRADE 2 MODERATE	GRADE 3 SEVERE	GRADE 4 POTENTIALLY LIFE- THREATENING
Sodium, High (mEq/L; mmol/L)	146 to < 150 146 to < 150	150 to < 154 150 to < 154	154 to < 160 154 to < 160	≥ 160 ≥ 160
Sodium, Low (mEq/L; mmol/L)	130 to < 135 130 to < 135	125 to < 130 125 to < 130	121 to < 125 121 to < 125	≤ 120 ≤ 120
Uric Acid, High (mg/dL; mmol/L)	7.5 to < 10.0 0.45 to < 0.59	10.0 to < 12.0 0.59 to < 0.71	12.0 to < 15.0 0.71 to < 0.89	≥ 15.0 ≥ 0.89

Hematology

PARAMETER	GRADE 1 MILD	GRADE 2 MODERATE	GRADE 3 SEVERE	GRADE 4 POTENTIALLY LIFE- THREATENING
Absolute CD4+ Count, Low (cell/mm ³ ; cells/L) > 5 years of age (not HIV infected)	300 to < 400 300 to < 400	200 to < 300 200 to < 300	100 to < 200 100 to < 200	< 100 < 100
Absolute Lymphocyte Count, Low (cell/mm ³ ; cells/L) > 5 years of age (not HIV infected)	600 to < 650 0.600×10^9 to < 0.650×10^9	500 to < 600 0.500×10^9 to < 0.600×10^9	350 to < 500 0.350×10^9 to < 0.500×10^9	< 350 < 0.350×10^9
Absolute Neutrophil Count (ANC), Low (cells/mm ³ ; cells/L) > 7 days of age	800 to 1,000 0.800×10^9 to 1.000×10^9	600 to 799 0.600×10^9 to 0.799×10^9	400 to 599 0.400×10^9 to 0.599×10^9	< 400 < 0.400×10^9
2 to 7 days of age	1,250 to 1,500 1.250×10^9 to 1.500×10^9	1,000 to 1,249 1.000×10^9 to 1.249×10^9	750 to 999 0.750×10^9 to 0.999×10^9	< 750 < 0.750×10^9
≤ 1 day of age	4,000 to 5,000 4.000×10^9 to 5.000×10^9	3,000 to 3,999 3.000×10^9 to 3.999×10^9	1,500 to 2,999 1.500×10^9 to 2.999×10^9	< 1,500 < 1.500×10^9
Fibrinogen, Decreased (mg/dL; g/L)	100 to < 200 1.00 to < 2.00 OR 0.75 to < 1.00 x LLN	75 to < 100 0.75 to < 1.00 OR ≥ 0.50 to < 0.75 x LLN	50 to < 75 0.50 to < 0.75 OR 0.25 to < 0.50 x LLN	< 50 < 0.50 OR < 0.25 x LLN OR Associated with gross bleeding
Hemoglobin¹⁶, Low (g/dL; mmol/L) ¹⁷ ≥ 13 years of age (male only)	10.0 to 10.9 6.19 to 6.76	9.0 to < 10.0 5.57 to < 6.19	7.0 to < 9.0 4.34 to < 5.57	< 7.0 < 4.34
≥ 13 years of age (female only)	9.5 to 10.4 5.88 to 6.48	8.5 to < 9.5 5.25 to < 5.88	6.5 to < 8.5 4.03 to < 5.25	< 6.5 < 4.03

¹⁶ Male and female sex are defined as sex at birth. For transgender participants ≥13 years of age who have been on hormone therapy for more than 6 consecutive months, grade hemoglobin based on the gender with which they identify (i.e., a transgender female should be graded using the female sex at birth hemoglobin laboratory values).

¹⁷ The most commonly used conversion factor to convert g/dL to mmol/L is 0.6206. For grading hemoglobin results obtained by an analytic method with a conversion factor other than 0.6206, the result must be converted to g/dL using appropriate conversion factor for the particular laboratory.

Hematology

PARAMETER	GRADE 1 MILD	GRADE 2 MODERATE	GRADE 3 SEVERE	GRADE 4 POTENTIALLY LIFE- THREATENING
57 days of age to < 13 years of age (male and female)	9.5 to 10.4 5.88 to 6.48	8.5 to < 9.5 5.25 to < 5.88	6.5 to < 8.5 4.03 to < 5.25	< 6.5 < 4.03
36 to 56 days of age (male and female)	8.5 to 9.6 5.26 to 5.99	7.0 to < 8.5 4.32 to < 5.26	6.0 to < 7.0 3.72 to < 4.32	< 6.0 < 3.72
22 to 35 days of age (male and female)	9.5 to 11.0 5.88 to 6.86	8.0 to < 9.5 4.94 to < 5.88	6.7 to < 8.0 4.15 to < 4.94	< 6.7 < 4.15
8 to ≤ 21 days of age (male and female)	11.0 to 13.0 6.81 to 8.10	9.0 to < 11.0 5.57 to < 6.81	8.0 to < 9.0 4.96 to < 5.57	< 8.0 < 4.96
≤ 7 days of age (male and female)	13.0 to 14.0 8.05 to 8.72	10.0 to < 13.0 6.19 to < 8.05	9.0 to < 10.0 5.59 to < 6.19	< 9.0 < 5.59
INR, High (not on anticoagulation therapy)	1.1 to < 1.5 x ULN	1.5 to < 2.0 x ULN	2.0 to < 3.0 x ULN	≥ 3.0 x ULN
Methemoglobin (% hemoglobin)	5.0 to < 10.0%	10.0 to < 15.0%	15.0 to < 20.0%	≥ 20.0%
PTT, High (not on anticoagulation therapy)	1.1 to < 1.66 x ULN	1.66 to < 2.33 x ULN	2.33 to < 3.00 x ULN	≥ 3.00 x ULN
Platelets, Decreased (cells/mm ³ ; cells/L)	100,000 to < 125,000 100.000×10^9 to < 125.000×10^9	50,000 to < 100,000 50.000×10^9 to < 100.000×10^9	25,000 to < 50,000 25.000×10^9 to < 50.000×10^9	< 25,000 < 25.000×10^9
PT, High (not on anticoagulation therapy)	1.1 to < 1.25 x ULN	1.25 to < 1.50 x ULN	1.50 to < 3.00 x ULN	≥ 3.00 x ULN
WBC, Decreased (cells/mm ³ ; cells/L)				
> 7 days of age	2,000 to 2,499 2.000×10^9 to 2.499×10^9	1,500 to 1,999 1.500×10^9 to 1.999×10^9	1,000 to 1,499 1.000×10^9 to 1.499×10^9	< 1,000 < 1.000×10^9
≤ 7 days of age	5,500 to 6,999 5.500×10^9 to 6.999×10^9	4,000 to 5,499 4.000×10^9 to 5.499×10^9	2,500 to 3,999 2.500×10^9 to 3.999×10^9	< 2,500 < 2.500×10^9

Urinalysis

PARAMETER	GRADE 1 MILD	GRADE 2 MODERATE	GRADE 3 SEVERE	GRADE 4 POTENTIALLY LIFE- THREATENING
Glycosuria (random collection tested by dipstick)	Trace to 1+ or ≤ 250 mg	2+ or > 250 to ≤ 500 mg	> 2+ or > 500 mg	NA
Hematuria (not to be reported based on dipstick findings or on blood believed to be of menstrual origin)	6 to < 10 RBCs per high power field	≥ 10 RBCs per high power field	Gross, with or without clots OR With RBC casts OR Intervention indicated	Life-threatening consequences
Proteinuria (random collection tested by dipstick)	1+	2+	3+ or higher	NA

Reference

U.S. Department of Health and Human Services, National Institutes of Health, National Institute of Allergy and Infectious Diseases, Division of AIDS. Division of AIDS (DAIDS) Table for Grading the Severity of Adult and Pediatric Adverse Events, Version 2.1. [March 2017]. Available from:

<https://rsc.tech-res.com/docs/default-source/safety/daids-ae-grading-table-mar2017.pdf>

12.4. Appendix 4: Adverse Events: Definitions and Procedures for Recording, Evaluating, Follow-up, and Reporting

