12.3.1. Estimating Severity Grade for Parameters Not Identified in the Grading Table

The functional table below should be used to grade the severity of an AE that is not specifically identified in the grading table. In addition, all deaths related to an AE are to be classified as grade 5.

PARAMETER	GRADE 1 MILD	GRADE 2 MODERATE	GRADE 3 SEVERE	GRADE 4 POTENTIALLY LIFE-THREATENING
Clinical adverse event NOT identified elsewhere in the grading table	Mild symptoms causing no or minimal interference with usual social & functional activities with intervention not indicated	Moderate symptoms causing greater than minimal interference with usual social & functional activities with intervention indicated	Severe symptoms causing inability to perform usual social & functional activities with intervention or hospitalization indicated	Potentially life-threatening symptoms causing inability to perform basic self-care functions with intervention indicated to prevent permanent impairment, persistent disability, or death

Major Clinical Conditions

Cardiovascular

PARAMETER	GRADE 1 MILD	GRADE 2 MODERATE	GRADE 3 SEVERE	GRADE 4 POTENTIALLY LIFE- THREATENING
Arrhythmia (by ECG or physical examination) Specify type, if applicable	No symptoms AND No intervention indicated	No symptoms AND Non-urgent intervention indicated	Non-life-threatening symptoms AND Non-urgent intervention indicated	Life-threatening arrhythmia OR Urgent intervention indicated
Blood Pressure Abnormalities¹ Hypertension (with the lowest reading taken after repeat testing during a visit) ≥ 18 years of age	140 to < 160 mmHg systolic OR 90 to < 100 mmHg diastolic	≥ 160 to < 180 mmHg systolic OR ≥ 100 to < 110 mmHg diastolic	≥ 180 mmHg systolic OR ≥ 110 mmHg diastolic	Life-threatening consequences in a participant not previously diagnosed with hypertension (e.g., malignant hypertension) OR Hospitalization indicated
< 18 years of age	> 120/80 mmHg	≥ 95 th to < 99 th percentile + 5 mmHg adjusted for age, height, and gender (systolic and/or diastolic)	≥ 99 th percentile + 5 mmHg adjusted for age, height, and gender (systolic and/or diastolic)	Life-threatening consequences in a participant not previously diagnosed with hypertension (e.g., malignant hypertension) OR Hospitalization indicated

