## 12.6.4. Safety

#### **Adverse Events**

#### **DAIDS Grading**

 Clinical adverse events will be graded based on the Division of AIDS Table for Grading the Severity of Adult and Pediatric Adverse Events Version 2.1, March 2017, as specified in the protocol Appendix 2.

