# 12.12.7. Safety Tables

Safety	Safety: Tables							
No.	Population	IDSL / Example Shell	Title	Programming Notes	Deliverable			
Advers	e Events (AE	s)						
3.01.	Safety	AE1	Summary of All Adverse Events by System Organ Class and Preferred Term		M12, M26, EOS			
3.02.	Safety	AE3	Summary of Common (>=5%) Adverse Events by Overall Frequency		M12, M26, EOS			
3.03.	Safety	AE3	Summary of Common (>=1%) Grade 2-4 Adverse Events by Overall Frequency		M12, M26, EOS			
3.04.	Safety	AE1	Summary All Drug-Related Adverse Events by System Organ Class		M12, M26, EOS			
3.05.	Safety	207966/primar y_02/T3.25	Summary of Subjects and Number of Occurrences of Common (>=5%) Non-Serious Adverse Events by System Organ Class	Add footnote: 'Note: Common adverse events are those with >=5% incidence in either treatment group.	M12, M26, EOS			
3.06.	Safety	AE3	Summary of Common (>=1%) Drug-Related Grade 2-4 Adverse Events by Overall Frequency	Add footnote: 'Note: Common adverse events are those with >=1% incidence in either treatment group.	M12, M26, EOS			
3.07.	Safety	207966/prima yr_02/T3.26	Summary of Subjects and Number of Occurrences of SAEs, Fatal SAEs, and Drug-related SAEs		HL, M12, M26, EOS			

Safety	: Tables				
No.	Population	IDSL / Example Shell	Title	Programming Notes	Deliverable
Other	Significant Ad	verse Events			
3.08.	Safety	AE1	Summary of Adverse Events Leading to Withdrawal/Permanent Discontinuation of Investigational Product by System Organ Class		HL, M12, M26, EOS
Labora	atory: Chemis	try and Hematol	ogy		•
3.09.	Safety	207966/primar y_02/T3.39	Summary of Chemistry Changes from Baseline by Visit		M12, M26, EOS
3.10.	Safety	207966/primar y_02/T3.41	Summary of Hematology Changes from Baseline by Visit		M12, M26, EOS
Labora	tory: Urinalys	sis			•
3.11.	Safety	207966/primar y_02/T3.48	Summary of Urine Concentration Changes from Baseline by Visit		M12, M26, EOS
Labora	atory: Hepatok	oiliary (Liver)			
3.12.	Safety	LIVER1	Summary of Liver Monitoring/Stopping Event Reporting		M12, M26, EOS
3.13.	Safety	207966/primar y_02/T3.57	Summary of Subjects Meeting Hepatobiliary Abnormality Criteria		M12, M26, EOS

Safety	Safety: Tables						
No.	Population	IDSL / Example Shell	Title	Programming Notes	Deliverable		
ECG							
3.14.	Safety	EG1	Summary of ECG Findings		M12, M26, EOS		
3.15.	Safety	207966/primar y_02/T3.61	Summary of QTc Values by Category		M12, M26, EOS		

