## 12.12.8. Safety Figures

Safety	: Figures				
No.	Population	IDSL / Example Shell	Title	Programming Notes	Deliverable
Advers	se Events				
3.01.	Safety	207966/primar y_02/F3.1	Plot of Common Adverse Events and Relative Risk – Q2M vs. DTG + RPV - Excluding Study Drug ISRs		M12, M26, EOS
Study	Drug Injection	Site Reaction A	dverse Events (display for Q2M arm only)		
3.02.	Safety	207966/primar y_02/F3.2	Plot of Common Study Drug Injection Site Reaction Adverse Events	Only display first panel	M12, M26, EOS
3.03.	Safety	207966/primar y_02/F3.3	Plot of Onset, Duration, and Severity of Overall and Common Study Drug Injection Site Reaction AEs by Maximum Grade - CAB and/or RPV		M12, M26, EOS
3.04.	Safety	207966/primar y_02/F3.4	Plot of Onset, Duration, and Severity of Overall and Common Drug-related Study Drug Injection Site Reaction AEs by Maximum Grade - CAB		M12, M26, EOS
3.05.	Safety	207966/primar y_02/F3.5	Plot of Onset, Duration, and Severity of Overall and Common Drug-related Study Drug Injection Site Reaction AEs by Maximum Grade - RPV		M12, M26, EOS
3.06.	Safety	207966/primar y_02/F3.6	Plot of Incidence of Maintenance Phase Study Drug Injection Site Reaction Adverse Events by Visit (Overall and Common) - CAB and/or RPV		M12, M26, EOS
3.07.	Safety	207966/primar y_02/F3.7	Plot of Incidence of Maintenance Phase Drug-Related Study Drug Injection Site Reaction Adverse Events by Visit (Overall and Common) - CAB		M12, M26, EOS

Safety	: Figures				
No.	Population	IDSL / Example Shell	Title	Programming Notes	Deliverable
3.08.	Safety	207966/primar y_02/F3.8	Plot of Incidence of Maintenance Phase Drug-Related Study Drug Injection Site Reaction Adverse Events by Visit (Overall and Common) - RPV		M12, M26, EOS
3.09.	Safety	207966/primar y_02/F3.9	Plot of Incidence of Grade 3-5 Maintenance Phase Study Drug Injection Site Reaction Adverse Events by Visit (Overall and Common) - CAB and/or RPV		M12, M26, EOS
3.10.	Safety	207966/primar y_02/F3.10	Plot of Incidence of Grade 3-5 Maintenance Phase Drug- related Study Drug Injection Site Reaction Adverse Events by Visit (Overall and Common) - CAB		M12, M26, EOS
3.11.	Safety	207966/primar y_02/F3.11	Plot of Incidence of Grade 3-5 Maintenance Phase Drug- related Study Drug Injection Site Reaction Adverse Events by Visit (Overall and Common) - RPV		M12, M26, EOS
Labora	itory				
3.12.	Safety	207966/primar y_02/F3.12	Scatter Plot of Maximum vs. Baseline for ALT		M12, M26, EOS

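### SAP Tables 3.03 and 3.06 stop at Grade 4, so a fatal adverse event (Grade 5 under the protocol) falls outside these two frequency tables while a Grade 2 event of the same term is kept

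*Protocol*

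**What the plan says.** - **Grading rule.** Protocol Section 12.3.1 (Appendix 3) states that "all deaths related to an AE are to be classified as grade 5". The scale in use therefore has five grades, although the printed grading tables show columns only for Grades 1 to 4.
- **Scale used in the analysis.** SAP Section 12.6.4: "Clinical adverse events will be graded based on the Division of AIDS Table for Grading the Severity of Adult and Pediatric Adverse Events Version 2.1". This is the scale in the protocol's Appendix 3. (The SAP cites it as protocol Appendix 2, which is a slip in the cross-reference.)
- **Table 3.03**, SAP Section 12.12.7: "Summary of Common (>=1%) Grade 2-4 Adverse Events by Overall Frequency". It has no programming note.
- **Table 3.06**, same section: "Summary of Common (>=1%) Drug-Related Grade 2-4 Adverse Events by Overall Frequency". Its only note defines the threshold: "Common adverse events are those with >=1% incidence in either treatment group".
- **Figure 3.09**, SAP Section 12.12.8: "Plot of Incidence of Grade 3-5 Maintenance Phase Study Drug Injection Site Reaction Adverse Events by Visit". Figures 3.10 and 3.11 use the same grade range for reactions attributed to CAB and to RPV.

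**The concern.** Tables 3.03 and 3.06 are, by title, the general frequency tables restricted to adverse events above Grade 1, for all causes and for drug-related events. A reader will take them to show everything worse than mild. A closed range of 2 to 4 instead applies a rule that keeps a moderate event and drops a fatal one of the same term. If the only case of a term above Grade 1 in the study is fatal, that term is absent from Table 3.03 and, if the event was judged drug-related, from Table 3.06 as well. A death counted in one table and missing from another, with no footnote to reconcile them, is an avoidable discrepancy about the most serious outcome.

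**Working it through.** The plan gives no figure to reproduce. The check compares the grading rule with the display specifications, and then asks whether the 1% threshold would remove a fatal event anyway.

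**1. Does the stated range admit Grade 5?**

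| Display | Scope | Grade range in title | Fatal event admitted by title? |
|---|---|---|---|
| Table 3.01 | All AEs, by system organ class and preferred term | none | yes |
| Table 3.03 | Common AEs | 2-4 | no |
| Table 3.06 | Common drug-related AEs | 2-4 | no |
| Table 3.07 | SAEs, with fatal SAEs named | none | yes |
| Table 3.47 | All AEs, by maximum toxicity | none | yes |
| Table 3.48 | Drug-related AEs, by maximum toxicity | none | yes, if drug-related |
| Figures 3.09-3.11 | Injection site reactions | 3-5 | yes |
| Listing 13 | All AEs | none | yes |
| Listing 15 | Fatal AEs | none | yes |

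Only Tables 3.03 and 3.06 exclude Grade 5 by title.

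**2. Is the cap or the threshold what removes the event?** For an arm of n participants, one event is 100/n percent, and the smallest count that reaches 1% is 0.01 × n rounded up. About 100 participants are planned in total (protocol Section 10.2). Participants choose their regimen, and the documents give no arm sizes, so n is an assumption and is shown as a range.

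| Assumed n in arm | One event | Count needed for 1% |
|---|---|---|
| 50 | 2.0% | 1 |
| 90 | 1.1% | 1 |
| 100 | 1.0% | 1 |
| 101 | 0.99% | 2 |
| 110 | 0.91% | 2 |

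In any arm of up to 100, a single event meets the threshold. At the planned size it is therefore the grade range, not rarity, that removes a lone fatal event.

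**3. Effect on a count.** As an illustration, take four participants in an arm of 100 with the same term and maximum grades of 2, 3, 4 and 5. Selecting Grades 2-4 counts 3 (3/100 = 3.0%). Selecting Grades 2-5 counts 4 (4/100 = 4.0%). The difference is the one fatal case.

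**4. Upper bound.** In Table 3.03 the shortfall for an arm is at most the number of participants with a fatal AE. In Table 3.06 it is at most the number with a drug-related fatal AE, since an unrelated death never belonged there. It is a bound because a participant who also had a Grade 2-4 record of the same term may still be counted, depending on a counting rule that the SAP does not show.

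**The case against.** **Deaths are reported elsewhere.** This is right, and it limits the point. A reader might infer that the SAP's severity reporting as a whole stops at Grade 4, or that deaths vanish from the report. The documents do not support either reading. Tables 3.47 and 3.48 present severity for all and for drug-related events with no stated cap, and both are headline deliverables, which Tables 3.03 and 3.06 are not. A term whose only case is fatal still appears by preferred term in Table 3.01. Table 3.07 and Listings 13 and 15 cover fatal events as well.

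**The size is easily overstated.** A reader might equate the shortfall with the number of fatal AEs in each arm. That is only the upper bound for Table 3.03, and Table 3.06 is touched only by drug-related deaths.

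**The titles may be shorthand.** The printed DAIDS tables have four columns, so 2-4 could be meant as Grade 2 and above, and the mock shells, available only on request, might handle Grade 5. This cannot be ruled out. But nothing printed in the SAP says so, and Figures 3.09 to 3.11 show that its authors write the upper bound as 5 when they mean to include it.

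**No rule is breached.** The SAP states no general upper-grade convention, and no hypothesis test or primary endpoint rests on these tables. That is true, and it is why the point is minor. It does not supply a reason to keep a Grade 2 event and drop a fatal one.

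**Conclusion.** The point holds for Tables 3.03 and 3.06 only. As titled, they apply the wrong upper grade for a scale that reserves Grade 5 for deaths related to an adverse event. If no such death occurs, the tables are unaffected. The conclusion assumes that the titles define the selection, which cannot be confirmed without the shells. The finding that one event would pass the 1% threshold also assumes an arm of no more than 100. This is a minor reporting correction, and the safety reporting as a whole still accounts for deaths.

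**What to change.** Change the title and the selection of SAP Tables 3.03 and 3.06 from Grade 2-4 to Grade 2-5, in line with protocol Section 12.3.1 and with the upper bound in Figures 3.09 to 3.11. When the shells are opened for this, confirm that Tables 3.47 and 3.48 have a place for Grade 5, and correct the SAP's reference for the DAIDS table from protocol Appendix 2 to Appendix 3.

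The cost is two titles and one selection condition. No data collection, endpoint or sample size changes, and there is no real downside.
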